**Figure 2: Proportion of Simulated Clinical Trial Subjects Anticipated to Meet or Exceed Target Trough Concentrations**

#### 5.4.1.3. Rationale for Proposed Doses: Part 4

The results of Part 3 will provide robust safety and efficacy data at BCX7353 doses of 125 and 250 mg QD. Both dose levels have been well-tolerated to date during a 28-day dosing regimen. Current safety data suggest that gastrointestinal AEs and liver enzyme abnormalities are dose-related, with the 125-mg dose level currently not associated with either finding and the 350-mg dose level most associated with these findings.

At all dose levels assessed in Parts 1 and 2, HAE attack rates were significantly reduced relative to placebo, with the greatest overall reduction observed at 125 mg QD, corresponding to ~4-fold  $EC_{50}$  on plasma kallikrein and a mean of 42% kallikrein inhibition at the end of a dosing interval. A closer evaluation of the attacks reported by 18 subjects receiving 350mg BCX7353 revealed that BCX7353 had a high degree of efficacy on peripheral attacks, with no effect on abdominal attacks, potentially due to mis-attribution of abdominal TEAEs as attacks. A 250 mg QD dose

did provide proportionally less exposure than a 350 mg dose, however kallikrein inhibition was generally indistinguishable over a dosing interval.

Therefore, the optimal BCX7353 dose is predicted to be one in which GI TEAEs are reduced but where effective plasma concentrations and kallikrein inhibition are maintained to prevent true HAE attacks from occurring. Based on available data this is likely to be in the 125 to 250 mg QD dose range. Following completion of enrollment in Part 3, Part 4 may be initiated in order to fully define the dose-response relationship with a dose intermediate to 125 and 250 mg. The decision to enroll Part 4, including the doses selected for Part 4, will be based on the PK, safety and efficacy results through Part 3 of the study.

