### 13.2.8. Pharmacokinetic/Pharmacodynamic Analyses

Exposure-response analyses of the relationships between plasma kallikrein inhibition, efficacy endpoints and BCX7353 plasma concentrations may be explored using model-based techniques as applicable.

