## 5. SAMPLE SIZE CONSIDERATIONS

Given that the BCX7353 response rate is unknown, the sample size was kept flexible to cover a range of response options that would achieve 90% power with an alpha of 0.05. The study population is expected to have a mean baseline attack rate of 1 attack/week. The expected mean reduction in attack rate of 350 mg BCX7353 QD is at least 70%. The mean reduction in attack rate in the placebo group may be as high as 30%. Sample size sensitivity assessments provided in Tables 2 and 3 are based on various BCX7353 and placebo responses and variability.

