**Table 2: Power assessment based on sample size and on-study attack rate**

Placebo			BCX7353			Power
Mean	SD	n	Mean	SD	N	
0.7	0.45	12	0.3	0.3	12	68%
0.7	0.45	12	0.3	0.45	12	55%
0.7	0.45	18	0.3	0.3	18	86%
0.7	0.45	18	0.3	0.45	18	74%
0.8	0.45	12	0.3	0.3	12	86%
0.8	0.45	12	0.3	0.4	12	79%
0.8	0.45	12	0.3	0.5	12	69%
0.8	0.45	18	0.3	0.3	18	97%
0.8	0.45	18	0.3	0.4	18	93%
0.8	0.45	18	0.3	0.5	18	87%

Note: Calculations were based on a 2-sided test at significance level of 0.05 and rates and SD are expressed in units.

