### **12.1. Statistical Analysis Methods**

#### **12.1.1. Analysis of Primary Efficacy Endpoint**

The primary efficacy endpoint is the number of confirmed HAE attacks in the FAS and PP populations. The number of HAE attacks will be analyzed by treatment group using appropriate descriptive statistics for the weekly attack rate, change and percentage change from baseline in attack rate, proportion of subjects with no attacks, and number of attack-free days. Efficacy analyses will be conducted for HAE attacks reported over the entire dosing interval (Days 1 to 28 inclusive) and during the effective dosing period in which BCX7353 should be at steady-state conditions (Days 8 to 28, inclusive). Efficacy endpoints will be summarized and listed for each treatment group.

Between-treatment comparisons (active vs. placebo and between active dose groups) for the weekly attack rate will be performed using an analysis of variance model and an analysis of covariance (ANCOVA) model. The adjusted qualifying attack rate will be included as a covariate in the ANCOVA model. The LSM for each treatment arm and the relative difference and associated 95% confidence intervals in attack rate between placebo and each active arm will also be calculated. If the difference between the 350mg and placebo is statistically significant,

additional dose response assessments will be analyzed based on the Tukey, Ciminera, and Heyse trend test.

The between treatment comparisons for the proportion of subjects who are attack free will be compared using a Fisher's exact test. If data warrant, a general linear model (Logistic regression) will also be used to test the dose response.

There will be no adjustments for multiplicity or previous interim analyses, if conducted, and all statistical tests will be 2-sided with an alpha of 0.05.

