### 14.2. Correlations of Dose or Drug Exposure with Pharmacodynamic Responses and Efficacy Outcomes

The following dose-response and exposure-response analyses of the relationships between pharmacokinetic, pharmacodynamic and efficacy measures will be explored using descriptive statistics, correlation assessment and model-based techniques as data permit:

- Correlation and exposure-response between plasma kallikrein inhibition and BCX7353 plasma concentrations
- Correlation and exposure-response between BCX7353 PK Parameters ( $C_{max}$ ,  $AUC_{tau}$ , mean  $C_{tau}$ ) and confirmed weekly HAE attack Rate
- Correlation between BCX7353 PK Parameters ( $C_{max}$ ,  $AUC_{tau}$ , mean  $C_{tau}$ ) and cleaved HK Change from baseline to the end of study and HK Follow-up/Baseline Ratio
- Correlation between the percent of plasma BCX7353 trough concentrations ( $C_{tau}$ ) above 4x and 8x kallikrein inhibition  $EC_{50}$  and confirmed attack rate

The correlation and exposure-response assessments will be presented graphically using a scatter plot along with the fitted regression line. Person correlation coefficient and p-value will be included on the plot.

- Plasma BCX7353 concentration, PK Parameters ( $C_{max}$ ,  $AUC_{tau}$ , mean  $C_{tau}$ ), and PD (HK, C1INH) data will be presented by attack free status

The PK and PD parameter will be summarized by subgroup based on attack free status for the subjects received the active BCX7353 dose. The between group difference will be estimate based on an ANCOVA model including fixed effect of subgroup. The qualifying attack rate will be included as a covariate.

- Comparison of confirmed attack rate between subgroup based on average plasma BCX7353 trough concentrations ( $C_{tau}$ ) above 4x and 8x kallikrein inhibition  $EC_{50}$  values

The confirmed attack rate will be summarized by subgroup based on the average plasma BCX7353 trough concentrations ( $C_{tau}$ ) for subjects received the active BCX7353 doses. The between group difference will be estimate based on an ANCOVA model including fixed effect of subgroup. The qualifying attack rate will be included as a covariate.

Additional PK-PD analysis may be explored as data permit.

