14.2.5.9	Summary of Percent of Ctrough above 8xEC50 and 8xEC80	PK
Pharmacodynamic Analysis		
14.2.6.1	Summary of Plasma Kallikrein Inhibition	KKI PD
14.2.6.2	Summary of Plasma Kallikrein Inhibition without Ellagic Acid Stimulation	KKI PD
14.2.6.3	Statistical Analysis of Plasma Kallikrein Inhibition	KKI PD
14.2.6.4	Statistical Analysis of Plasma Kallikrein Inhibition without Ellagic Acid Stimulation	KKI PD
14.2.6.5	Summary of C1INH Functional and C4 Levels	C1INH PD
14.2.6.6	Summary of Cleaved HK Fragments	Cleaved HK PD
14.2.6.7	Statistical Analysis of Cleaved HK Fragments	Cleaved HK PD
14.2.6.8	Summary of BMP Levels	BMP PD

Tables	Title	Population
PKPD/Efficacy Analysis (PK-PD include subjects with measurements for both PK-PD/Efficacy data)		
14.2.7.1	Summary of Plasma Kallikrein Inhibition by Attack Free Response	KKI PD
14.2.7.2	Summary of Plasma BCX7353 Concentration by Attack Free Response	PK
14.2.7.3	Summary of Trough BCX7353 Concentration by Attack Free Response	PK
14.2.7.4	Summary of Derived Plasma BCX7353 Pharmacokinetic Parameters by Attack Free Response	PK
14.2.7.5	Summary of cleaved HK levels by Attack Free Response	HK PD
14.2.7.6	Summary of C1INH and C4 levels by Attack Free Response	C1INH PD
Additional PKPD and Efficacy analyses maybe performed if data permit.		
Safety		
14.3.1.1.1	Summary of Treatment Exposure	Safety
14.3.1.1.2	Summary of Study Drug Compliance – Drug Accountability	Safety
14.3.1.2	Overall Summary of Treatment-Emergent Adverse Events	Safety
14.3.1.3	Summary of Treatment-Emergent Adverse Events	Safety
14.3.1.4	Summary of Drug-related Treatment-Emergent Adverse Event	Safety
14.3.1.5	Summary of Treatment-Emergent Adverse Events by severity	Safety
14.3.1.6	Summary of Treatment-Emergent Grade 3 or Grade 4 Adverse Events	Safety
	Summary of Drug-related Treatment-Emergent Grade 3 or Grade 4 Adverse Events	Safety
14.3.1.7	Summary of Treatment-Emergent Serious Adverse Events	Safety
14.3.1.8	Summary of Treatment-Emergent Adverse Events leading to Permanent Discontinuation of Study Drug	Safety
14.3.1.9	Summary of Treatment-Emergent Adverse Events leading to Interruption of Study Drug	Safety
14.3.1.10	Summary of Drug-related Treatment-Emergent Serious Adverse Event	Safety
14.3.1.11	Summary of Treatment-Emergent Rashes Considered Related to Study Drug	Safety
14.3.5.1	Summary of Laboratory Values by Visit – Hematology	Safety
14.3.5.2	Summary of Laboratory Values by Visit – Chemistry	Safety

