14.2.1.4	Plot of Individual Attack Rate by Treatment – Subject Reported Attack	FAS
14.2.1.5	Plot of Confirmed Attack and Acute HAE Medications	FAS
14.2.1.6	Plot of Qualifying Attack Rate (Histogram Plot)	FAS
14.2.1.7	Plot of Individual Attack Rate Overtime (Line plot for each subject)	FAS
14.2.1.8	Plot of On-study Confirmed Attack Rate vs Qualifying Attack Rate	FAS
14.2.1.9	Plot of Difference between On-study Confirmed Attack Rate and Qualifying Attack Rate vs Qualifying Attack Rate	FAS
14.2.1.10	Plot of Percentage of Difference between On-study Confirmed Attack Rate and Qualifying Attack Rate vs Qualifying Attack Rate	FAS
14.2.1.11	KM Plot of Time to First Attack after Last Dose	FAS
14.2.1.12	KM Plot of Time to First Attack after First Dose	FAS
14.2.1.13	KM Plot of Time to Treatment	FAS
14.2.1.XX	Correlation Plots of AE-QoL, DASS and Confirmed Attack endpoints (will plot the domains with significant correlation at P<0.10)	FAS
Pharmacokinetic Analysis		
14.2.2.1	Mean Plasma BCX7353 Concentration-time plot –linear Scale	PK
14.2.2.2	Mean Plasma BCX7353 Concentration-time plot – semi-logarithmic scale	PK
14.2.2.3	Median Plasma BCX7353 Concentration-time plot –linear Scale	PK
14.2.2.4	Median Plasma BCX7353 Concentration-time plot – semi-logarithmic scale	PK
14.2.2.5	Individual Plasma BCX7353 Concentration-time plot –linear Scale	PK
14.2.2.6	Individual Plasma BCX7353 Concentration-time plot - semi-logarithmic scale	PK
14.2.2.7	Mean Trough Plasma BCX7353 Concentration-time plot –linear Scale	PK
14.2.2.8	Median Trough Plasma BCX7353 Concentration-time plot –linear Scale	PK
14.2.2.8	Individual Trough Plasma BCX7353 Concentration-time plot (line plot)	PK

Figures	Title	Population
Pharmacodynamic Analyses		
14.2.3.1	Plot of Mean Ex-vivo Kallikrein Inhibition - Time Profile by Treatment	PD
14.2.3.2	Plot of Individual Ex-vivo Kallikrein Inhibition - Time Profile by Treatment	PD
14.2.3.3	Plot of Least Squares Mean of Treatment Differences from Placebo in Ex-vivo Kallikrein Inhibition	PD
Pharmacokinetic/Pharmacodynamic Analyses (PK-PD include subjects with measurements for both PK-PD)		
14.2.4.1	Plot of Plasma Kallikrein Inhibition and Plasma BCX7353 Concentration	KKI PD
14.2.4.2	Exposure-response Analysis of Ex-vivo Kallikrein Inhibition	KKI PD
14.2.4.3	Plot of Plasma Kallikrein Inhibition by Attack Free Status	KKI PD

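### SAP 14.2 relates kallikrein inhibition, cleaved HK and C1 INH to efficacy only as attack-free yes/no, although every subject's attack rate is derived and is used for PK and quality of life

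*SAP*

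**What the plan says.** SAP 14.2 treats PK and PD differently.

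- **PK.** Cmax, AUCtau, mean Ctau and the percentage of troughs above 4x and 8x EC50 are correlated with the confirmed weekly attack rate. The rate is also compared between subjects above and below those trough thresholds.
- **Cleaved HK and C1 INH.** These are compared by attack-free status, in active subjects, by ANCOVA with the qualifying attack rate as covariate: "The PK and PD parameter will be summarized by subgroup based on attack free status for the subjects received the active BCX7353 dose".
- **Kallikrein inhibition.** It is not named in that bullet. It meets efficacy only in Table 14.2.7.1, "Summary of Plasma Kallikrein Inhibition by Attack Free Response", and Figure 14.2.4.3, "Plot of Plasma Kallikrein Inhibition by Attack Free Status". Tables 14.2.7.5 and 14.2.7.6 and Figures 14.2.4.11 and 14.2.4.12 do the same for HK and C1 INH.

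SAP 10.8.1 derives a weekly attack rate for each subject. SAP 12.1.4.2 correlates AE-QoL and DASS with it. Protocol 13.2.8 leaves more work open: "Exposure-response analyses of the relationships between plasma kallikrein inhibition, efficacy endpoints and BCX7353 plasma concentrations may be explored". SAP 14.2 closes with a similar optional sentence.

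**The concern.** The attack-free split puts a subject with one attack in the same group as a subject with six. It yields a difference in mean marker level between two outcome groups, not the change in attack rate per unit of marker.

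That second quantity bears on the protocol's dose argument. Protocol 5.4.1.3 looks for a dose at which "effective plasma concentrations and kallikrein inhibition are maintained to prevent true HAE attacks from occurring", and places 175 mg at a predicted 62% inhibition, between 42% at 125 mg and 76% at 250 mg. Whether inhibition tracks attacks is the link this argument needs. The SAP gives no reason for using the full outcome scale for PK and quality of life but not for PD.

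**Working it through.** **Inputs from the documents**
- Level: SAP 12.1.1 says "all statistical tests will be 2-sided with an alpha of 0.05", without multiplicity adjustment.
- Active subjects in the SAP's three parts: 36 x 1/2 = 18, 14 x 6/7 = 12 and 20 x 9/10 = 18, total 48 (18/12/12/6 on 350/250/125/62.5 mg).
- Planned rate: SAP 5 says "The study population is expected to have a mean baseline attack rate of 1 attack/week". A 70% reduction leaves 0.3/week, or 0.3 x 4 = 1.2 attacks per 28 days.
- Interim active rate (Protocol 5.3.3.3): 0.898 - 0.434 = 0.464/week, or 1.86 per 28 days.
- Planned attack-free proportion on active: 70-85% (SAP Table 3).

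**The plan's own figures first.** The note to SAP Table 2 reads "Calculations were based on a 2-sided test at significance level of 0.05". For 0.8 (SD 0.45) vs 0.3 (SD 0.3), 18 per arm: SD = sqrt((0.45^2 + 0.3^2)/2) = 0.382; noncentrality = (0.5/0.382) x sqrt(18/2) = 3.92; 34 df; power 96.8%, against 97% stated. All ten rows reproduce within 1 point. No power is stated for any PD-efficacy analysis.

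**Loss from the split.** The documents give no PD-efficacy effect size, marker SD or count dispersion, so these are assumed: a standard-normal marker, log attack rate linear in it, and Poisson or gamma-Poisson 28-day counts (dispersion 0, 0.5 or 1.2). The slope is set so that Pearson correlation on the attack rate has about 80% power at n = 48. The split is a t-test of the marker by attack-free status, without the SAP's covariate.

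| Mean attacks/28 d | Dispersion | Attack-free | Split | Pearson | Spearman | Loss vs Pearson | Loss vs Spearman |
|---|---|---|---|---|---|---|---|
| 0.25 | 0 | 80% | 74% | 79% | 73% | 5 | -1 |
| 0.3 | 1.2 | 83% | 75% | 81% | 75% | 6 | 0 |
| 0.4 | 0 | 70% | 71% | 80% | 73% | 9 | 2 |
| 1.2 | 0 | 33% | 49% | 79% | 73% | 30 | 23 |
| 1.2 | 0.5 | 43% | 53% | 81% | 72% | 28 | 19 |
| 1.2 | 1.2 | 53% | 55% | 80% | 71% | 25 | 15 |
| 1.86 | 0 | 18% | 35% | 80% | 74% | 45 | 39 |
| 1.86 | 0.5 | 31% | 42% | 80% | 71% | 38 | 29 |
| 1.86 | 1.2 | 43% | 48% | 80% | 71% | 32 | 23 |

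When most subjects have no attack, the count carries little more than the split, so the loss is small. Over fixed effects and n = 31, 48 and 66 the loss against Pearson ran from 1 to 45 points.

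**Check against the interim dose pattern.** Protocol 5.3.3.3 implies 0.898 - 0.579 = 0.319/week at 125 mg, 0.898 - 0.417 = 0.481 at 250 mg and 0.898 - 0.384 = 0.514 at 350 mg. The 250-to-125 mg ratio is 0.481/0.319 = 1.5: more attacks with more inhibition. I assumed mean inhibition of 42/76/80% (80% is my figure), between-subject SD 10-20 points and 12/12/18 subjects. Both tests then rejected in only about 6-23% of runs. The gap lay between about 1 point in favour of the split and 8 in favour of the count, and nearly all rejections pointed that way round.

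By contrast, if the rate halved between 42% and 76% inhibition (mean 0.3/week, SD 0.3, with 25% inhibition assumed at 62.5 mg), power would be 58-72% for the split and 90-96% for the count. Type I error was near 5% for both.

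**The case against.** **Other routes exist.** Protocol 13.2.8 names kallikrein inhibition together with efficacy endpoints, and SAP 14.2 and 16 allow added analyses and figures. A reader might infer that the plan rules out a PD-versus-rate analysis; it does not. But permission leaves the marker summary, time point and model unspecified.

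**Kallikrein inhibition is partly covered.** The SAP models inhibition on concentration and relates PK and troughs above EC50 to the attack rate. Protocol 5.3.3.2 reports r = 0.85 between exposure and inhibition. This stands, but only in part: 0.85^2 = 0.72 of variance is shared, the relationship is sigmoidal, and Protocol 5.4.1.3 finds inhibition hard to tell apart between 250 and 350 mg although exposure differs. For HK there is only a PK-HK correlation. For C1 INH no such cover is documented.

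**The simulated test is not exactly the SAP's.** The ANCOVA covers HK and C1 INH and has a covariate; kallikrein inhibition is only summarised and plotted. A reader might infer that inhibition is formally tested by attack-free status. The documents do not say so.

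**Total attacks may mislead.** Protocol 5.3.3.1, 5.3.3.3 and 5.4.1.3 say GI side effects may be misattributed as abdominal attacks. At 350 mg peripheral attacks fell 72.0% while abdominal attacks rose 1.9%. A regression on all attacks could absorb this, so the fix needs a location split.

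**Active-only is defensible.** SAP 14.1 shows that placebo subjects have PD data, but pooling them mixes inhibition with treatment assignment. Leaving them out of the main analysis is not an error.

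**Conclusion.** The point holds for what the SAP specifies: all three PD markers meet efficacy only through attack-free yes/no, while the per-subject rate exists and is used elsewhere. The analysis is exploratory, so the consequence is a weaker and less usable estimate.

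A reader might infer one fixed power loss. The documents do not support that, because its size depends on the attack-free proportion and on assumptions they do not give. With the count analysis at 80% power and n = 48, it is about 5-9 points at the 70-85% attack-free of SAP Table 3 (essentially none against Spearman), 25-30 at 0.3/week (15-23 against Spearman) and 32-45 at 0.464/week. The first case fits poorly with the interim mean: 70% attack-free at 1.86 attacks per 28 days would need the other 30% to average 1.86/0.3 = 6.2 attacks, or 1.55/week, against a placebo mean of 0.898.

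A reader might also infer that the count analysis would have shown inhibition reducing attacks across these doses. The interim pattern runs the other way, in small groups (6 at 250 mg, 7 at 125 mg), and there the gain is small.

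**What to change.** Add one bullet to SAP 14.2, parallel to the PK one:

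- A scatter plot, rank correlation and overdispersed count regression of the confirmed attack count (log days as offset, adjusted qualifying attack rate as covariate) on steady-state kallikrein inhibition, cleaved HK change from baseline and C1 INH change from baseline.
- Active subjects as the main display, with placebo added as a secondary one.
- The same analyses for peripheral and abdominal attacks separately, a split SAP 12.1.4 already uses.
- The existing attack-free tables and figures kept as descriptive displays.

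This needs no new assessments or subjects. The cost is a few more exploratory outputs, unadjusted for multiplicity like the rest, and SAP 11.3 already provides for revisions to the plan.

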## 16. TABLES, FIGURES AND LISTINGS

Tables	Title	Population
Study Population		
14.1.1	Summary of Study Disposition	All Subjects
14.1.2	Summary of Study Disposition by Country and Site	Safety
14.1.2	Summary of Study Completion	Safety
14.1.3.1	Summary of Demography	FAS
14.1.3.2	Summary of Demography	PP
14.1.3.3	Summary of Demography	Safety
14.1.3.4	Summary of Sub-groups	Safety
14.1.3.5	Summary of Medical History	Safety
14.1.4.1	Summary of Concomitant Medications	Safety
14.1.4.2	Summary of Concomitant Medications for HAE	Safety
14.1.5.1	HAE Demography – HAE History	Safety
14.1.5.2	HAE Demography – Past on-Demand Treatments of HAE	Safety
14.1.5.3	HAE Demography – Current on-Demand Treatments of HAE	Safety
14.1.5.4	HAE Demography – Past Prophylactic Treatments of HAE	Safety
14.1.5.5	Summary of Pretreatment Attack Rate (include Subject reported qualifying rate, adjusted qualifying rate, Screening attack rate)	Safety
14.1.5.6	Summary of Attack Confirmation	Safety
14.1.6.1	Summary of Inclusion/Exclusion Criteria Deviations	Safety
14.1.6.2	Summary of Protocol Deviation	Safety
Efficacy Tables for Entire Dosing Period and Entire Study Period All tables will be repeated for the PP population Table Numbering: FAS tables will end as .1; PP tables will end as .2		
14.2.1.1.1	Overall Attack Summary during Entire Dosing Period	FAS
14.2.1.1.2	Overall Attack Summary during Entire Dosing Period	PP
14.2.1.1.3	Overall Attack Summary during Entire Study Period	FAS
14.2.1.1.4	Overall Attack Summary during Entire Study Period	PP
14.2.1.2	Summary of Rate of Confirmed Attacks during Entire Dosing Period (include the difference from the adjusted qualifying rate on the same table)	FAS/PP
14.2.1.2.3	Summary of Rate of Confirmed Attacks during Entire Study Period (include the difference from the adjusted qualifying rate on the same table)	FAS
14.2.1.2.4	Summary of Rate of Confirmed Attacks during Entire Study Period (include the difference from the adjusted qualifying rate on the same table)	PP
14.2.1.3	Summary of Number of Confirmed Attacks by Week during Entire Dosing Period	FAS/PP
14.2.1.4	Summary of Rate of Confirmed Attacks Requiring Treatment during Entire Dosing Period	FAS/PP
14.2.1.5	Summary of Rate of Confirmed Abdominal Attacks during Entire Dosing Period	FAS/PP
14.2.1.6	Summary of Rate of Confirmed Peripheral Attacks during Entire Dosing Period	FAS/PP

Tables	Title	Population
	Period	
14.2.1.7	Summary of Rate of Subject-Reported Attacks during Entire Dosing Period	FAS/PP
14.2.1.8	Statistical Analysis of Rate of Confirmed Attacks during Entire Dosing Period	FAS/PP
14.2.1.8.3	Statistical Analysis of Rate of Confirmed Attacks during Entire Study Period	FAS
14.2.1.8.4	Statistical Analysis of Rate of Confirmed Attacks during Entire Study Period	PP
14.2.1.9	Statistical Analysis of Rate of Confirmed Attacks during Entire Dosing Period - Poisson-regression Model	FAS/PP
14.2.1.10	Statistical Analysis of Rate of Confirmed Attacks Requiring Treatment during Entire Dosing Period	FAS/PP
14.2.1.11	Sensitivity Statistical Analysis of Rate of Confirmed Attacks Excluding Missing Diary Days during Entire Dosing Period	FAS/PP
14.2.1.12	Sensitivity Statistical Analysis of Rate of Confirmed Attacks during Entire Dosing Period (BOCF)	FAS/PP
14.2.1.13	Statistical Analysis of Rate of Confirmed Abdominal Attacks during Entire Dosing Period	FAS/PP
14.2.1.14	Statistical Analysis of Rate of Confirmed Peripheral Attacks during Entire Dosing Period	FAS/PP
14.2.1.15	Statistical Analysis of Rate of Subject-Reported Attacks during Entire Dosing Period (subject reported qualifying rate will be used as covariate)	FAS/PP
14.2.1.16	Summary of Proportion of Subjects who are Attack-free during Entire Dosing Period (include sensitivity analyses of missing=failure; missing=excluded )	FAS/PP
14.2.1.16.3	Summary of Proportion of Subjects who are Attack-free during Entire Study Period (include sensitivity analyses of missing=failure; missing=excluded )	FAS
14.2.1.16.4	Summary of Proportion of Subjects who are Attack-free during Entire Study Period (include sensitivity analyses of missing=failure; missing=excluded )	PP
14.2.1.17	Summary of Number of Attack-free days during Entire Dosing Period	FAS/PP
14.2.1.18	Summary of Percent of Attack-free days during Entire Dosing Period	FAS/PP
14.2.1.19	Statistical Analysis of Number of Attack-free days during Entire Dosing Period	FAS/PP
14.2.1.20	Statistical Analysis of Percent of Attack-free days during Entire Dosing Period	FAS/PP
14.2.1.21	Assessment of Dose Response - Entire Dosing Period	FAS/PP
Efficacy Tables for Effective Dosing Period		
All tables will be repeated for the PP population		
Table Numbering: FAS tables will end as .1; PP tables will end as .2		
14.2.2.1	Overall Attack Summary during Effective Dosing Period	FAS/PP
14.2.2.2	Summary of Rate of Confirmed Attacks during Effective Dosing Period (include the difference from qualifying on the same table)	FAS/PP
14.2.2.3	Summary of Number of Confirmed Attacks by Week during Effective Dosing Period	FAS/PP
14.2.2.4	Summary of Rate of Confirmed Attacks Requiring Treatment during Effective Dosing Period	FAS/PP
14.2.2.5	Summary of Rate of Confirmed Abdominal Attacks during Effective Dosing	FAS/PP

Tables	Title	Population
	Period	
14.2.2.6	Summary of Rate of Confirmed Peripheral Attacks during Effective Dosing Period	FAS/PP
14.2.2.7	Summary of Rate of Subject-Reported Attacks during Effective Dosing Period	FAS/PP
14.2.2.8	Statistical Analysis of Rate of Confirmed Attacks during Effective Dosing Period	FAS/PP
14.2.2.9	Statistical Analysis of Rate of Confirmed Attacks during Effective Dosing Period - Poisson-regression Model	FAS/PP
14.2.2.10	Statistical Analysis of Rate of Confirmed Attacks Requiring Treatment during Effective Dosing Period	FAS/PP
14.2.2.11	Sensitivity Statistical Analysis of Rate of Confirmed Attacks Excluding Missing Diary Days during Effective Dosing Period	FAS/PP
14.2.2.12	Sensitivity Statistical Analysis of Rate of Confirmed Attacks during Effective Dosing Period (BOCF)	FAS/PP
14.2.2.13	Statistical Analysis of Rate of Confirmed Abdominal Attacks during Effective Dosing Period	FAS/PP
14.2.2.14	Statistical Analysis of Rate of Confirmed Peripheral Attacks during Effective Dosing Period	FAS/PP
14.2.2.15	Statistical Analysis of Rate of Subject-Reported Attacks during Effective Dosing Period (subject reported qualifying rate will be used as covariate)	FAS/PP
14.2.2.16	Summary of Proportion of Subjects who are Attack-free during Effective Dosing Period (include sensitivity analyses of missing=failure; missing=excluded )	FAS/PP
14.2.2.17	Summary of Number of Attack-free days during Effective Dosing Period	FAS/PP
14.2.2.18	Summary of Percent of Attack-free days during Effective Dosing Period	FAS/PP
14.2.2.19	Statistical Analysis of Number of Attack-free days during Effective Dosing Period	FAS/PP
14.2.2.20	Statistical Analysis of Percent of Attack-free days during Effective Dosing Period	FAS/PP
14.2.2.21	Assessment of Dose Response - Effective Dosing Period	FAS/PP
The following will be provided for the Entire Dosing Period		
All tables will be repeated for the PP population		
Table Numbering: FAS tables will end as .1; PP tables will end as .2		
14.2.3.1.1	Summary of Time intervals between Attacks	FAS/PP
14.2.3.2	Summary of AAS Categorical Response -Attack level	FAS/PP
14.2.3.3	Summary of AAS Categorical Response -Subject level (worst response for each AAS question)	FAS/PP
14.2.3.4	Summary of AAS Total Score (include AAS total and Domain Total Score)	FAS/PP
14.2.3.5	Statistical Analysis of AAS Total Score (include AAS total and Domain Total Score)	FAS/PP
14.2.3.6	Summary of Attack Duration at Subject Level – Confirmed Attacks	FAS/PP
14.2.3.7	Summary of Attack Duration of All Confirmed Attacks	FAS/PP
14.2.3.8	Summary of Attack Triggers – Confirmed Attacks	FAS/PP
14.2.3.9	Summary of Attack Symptoms – Confirmed Attacks	FAS/PP
14.2.3.10	Summary of Number of Symptoms – Confirmed Attacks	FAS/PP

Tables	Title	Population
14.2.3.11	Summary of Attack Location – Confirmed Attacks	FAS/PP
14.2.3.12	Summary of Attack Onset time from the last dose– Confirmed Attacks	FAS/PP
14.2.3.13	Summary of Administrations of Acute HAE Medications – Confirmed Attacks	FAS/PP
14.2.3.14	Number and Percentage of Attacks Requiring Additional Medical Care	FAS/PP
14.2.3.15	Summary of time to treatment –Confirmed Attacks (overall, by country and by site )	FAS/PP
14.2.3.16	Time to Treatment (KM estimates)	FAS/PP
14.2.3.17	Summary of Qualifying, Screening Attack and Post Treatment HAE attack Rate	FAS/PP
14.2.3.18	Statistical Analysis of Post Treatment HAE attack Rate	FAS/PP
14.2.3.19	Time of First Attack after the First Dose (KM estimates)	FAS/PP
14.2.3.20	Time of First Attack after Last Dose (KM estimates)	FAS/PP
14.2.4.1	Summary of AeQoL scores	FAS/PP
14.2.4.2	Statistical Analysis of AeQoL Scores	FAS/PP
14.2.4.3	Correlation among AeQoL and Attack Rate	FAS/PP
14.2.4.4	Summary of DASS Severity-Rating Index Categories	FAS/PP
14.2.4.5	Summary of DASS scores	FAS/PP
14.2.4.6	Correlation among DASS Domains and Attack Rate	FAS/PP
14.2.4.7	Correlation between AeQoL and DASS Domains	FAS/PP
14.2.5.1	Statistical Analysis of DASS Scores	FAS/PP
Pharmacokinetic Analysis		
14.2.5.2	Summary of Plasma BCX7353 Concentration	PK
14.2.5.3	Summary of Derived Plasma BCX7353 Pharmacokinetic Parameters	PK
14.2.5.4	Summary of Trough BCX7353 Concentration	PK
14.2.5.5	Assessment of Dose Proportionality based on Power Model	PK
14.2.5.6	Assessment of Dose Proportionality based on ANOVA	PK
14.2.5.7	Assessment of Steady State	PK
14.2.5.8	Number and Percent of Average Ctrough above 4xEC50 and 4xEC80	PK
14.2.5.9	Summary of Percent of Ctrough above 8xEC50 and 8xEC80	PK
Pharmacodynamic Analysis		
14.2.6.1	Summary of Plasma Kallikrein Inhibition	KKI PD
14.2.6.2	Summary of Plasma Kallikrein Inhibition without Ellagic Acid Stimulation	KKI PD
14.2.6.3	Statistical Analysis of Plasma Kallikrein Inhibition	KKI PD
14.2.6.4	Statistical Analysis of Plasma Kallikrein Inhibition without Ellagic Acid Stimulation	KKI PD
14.2.6.5	Summary of C1INH Functional and C4 Levels	C1INH PD
14.2.6.6	Summary of Cleaved HK Fragments	Cleaved HK PD
14.2.6.7	Statistical Analysis of Cleaved HK Fragments	Cleaved HK PD
14.2.6.8	Summary of BMP Levels	BMP PD

Tables	Title	Population
PKPD/Efficacy Analysis (PK-PD include subjects with measurements for both PK-PD/Efficacy data)		
14.2.7.1	Summary of Plasma Kallikrein Inhibition by Attack Free Response	KKI PD
14.2.7.2	Summary of Plasma BCX7353 Concentration by Attack Free Response	PK
14.2.7.3	Summary of Trough BCX7353 Concentration by Attack Free Response	PK
14.2.7.4	Summary of Derived Plasma BCX7353 Pharmacokinetic Parameters by Attack Free Response	PK
14.2.7.5	Summary of cleaved HK levels by Attack Free Response	HK PD
14.2.7.6	Summary of C1INH and C4 levels by Attack Free Response	C1INH PD
Additional PKPD and Efficacy analyses maybe performed if data permit.		
Safety		
14.3.1.1.1	Summary of Treatment Exposure	Safety
14.3.1.1.2	Summary of Study Drug Compliance – Drug Accountability	Safety
14.3.1.2	Overall Summary of Treatment-Emergent Adverse Events	Safety
14.3.1.3	Summary of Treatment-Emergent Adverse Events	Safety
14.3.1.4	Summary of Drug-related Treatment-Emergent Adverse Event	Safety
14.3.1.5	Summary of Treatment-Emergent Adverse Events by severity	Safety
14.3.1.6	Summary of Treatment-Emergent Grade 3 or Grade 4 Adverse Events	Safety
	Summary of Drug-related Treatment-Emergent Grade 3 or Grade 4 Adverse Events	Safety
14.3.1.7	Summary of Treatment-Emergent Serious Adverse Events	Safety
14.3.1.8	Summary of Treatment-Emergent Adverse Events leading to Permanent Discontinuation of Study Drug	Safety
14.3.1.9	Summary of Treatment-Emergent Adverse Events leading to Interruption of Study Drug	Safety
14.3.1.10	Summary of Drug-related Treatment-Emergent Serious Adverse Event	Safety
14.3.1.11	Summary of Treatment-Emergent Rashes Considered Related to Study Drug	Safety
14.3.5.1	Summary of Laboratory Values by Visit – Hematology	Safety
14.3.5.2	Summary of Laboratory Values by Visit – Chemistry	Safety
14.3.5.3	Summary of Laboratory Values by Visit – Urinalysis	Safety
14.3.5.4	Summary of Graded Shift in Laboratory Abnormalities - Hematology	Safety
14.3.5.5	Summary of Graded Shift in Laboratory Abnormalities – Chemistry	Safety
14.3.5.6	Summary of Treatment-Emergent Laboratory Abnormalities	Safety
14.3.5.7	Summary of Treatment-Emergent Grade 3 and 4 Laboratory Abnormalities	Safety
14.3.5.8	Summary of Lab Toxicity Grade Increase from Baseline	Safety
14.3.6.1	Summary of Vital Signs by Visit	Safety
14.3.6.2	Summary of Body Weight by Visit	Safety
14.3.6.3	Summary of QTcF Categorical Findings by Visit	Safety
14.3.6.4	Summary of 12-lead Electrocardiograms Parameters by Visit	Safety
14.3.6.5	Summary of 12-lead Electrocardiograms Assessment by Visit	Safety
14.3.6.6	Summary of Pulmonary Diffusion data by Visit	Safety
14.3.6.7.1	Summary of Fold x ULN for Liver Function Tests	Safety

Tables	Title	Population
14.3.6.7.2	Summary of Fold x ULN for Liver Function Tests –Subjects with Prior Androgen Use	Safety
14.3.6.7.3	Summary of Fold x ULN for Liver Function Tests –Subjects without Prior Androgen Use	Safety
14.3.6.8.1	Summary of Fold x from Baseline for Liver Function Tests	Safety
14.3.6.8.2	Summary of Fold x from Baseline for Liver Function Tests –Subjects with Prior Androgen Use	Safety
14.3.6.8.3	Summary of Fold x from Baseline for Liver Function Tests –Subjects without Prior Androgen Use	Safety
14.3.6.9.1	Summary of Number of Subjects with Elevations in Post Baseline Liver Function Tests	Safety
14.3.6.9.2	Summary of Number of Subjects with Elevations in Post Baseline Liver Function Tests –Subjects with Prior Androgen Use	Safety
14.3.6.9.3	Summary of Number of Subjects with Elevations in Post Baseline Liver Function Tests –Subjects without Prior Androgen Use	Safety

Figures	Title	Population
Study population		
14.1.1	Consort Diagram	All subjects
14.1.2	Time to study drug discontinuation	RS
Efficacy		
All Efficacy Figure will be repeated for the PP population		
Table Numbering: FAS tables will end as .1; PP tables will end as .2		
14.2.1.1	Plot of Estimated Treatment Effect (If data permit, Forest plot to show estimated between treatment difference and 95%CI, for overall and by each subgroup)	FAS
14.2.1.2	Plot of Individual Attack Rate by Treatment –Confirmed Attack	FAS
14.2.1.3	Cumulative Distribution Function of the Confirmed Attack Rate	FAS
14.2.1.4	Plot of Individual Attack Rate by Treatment – Subject Reported Attack	FAS
14.2.1.5	Plot of Confirmed Attack and Acute HAE Medications	FAS
14.2.1.6	Plot of Qualifying Attack Rate (Histogram Plot)	FAS
14.2.1.7	Plot of Individual Attack Rate Overtime (Line plot for each subject)	FAS
14.2.1.8	Plot of On-study Confirmed Attack Rate vs Qualifying Attack Rate	FAS
14.2.1.9	Plot of Difference between On-study Confirmed Attack Rate and Qualifying Attack Rate vs Qualifying Attack Rate	FAS
14.2.1.10	Plot of Percentage of Difference between On-study Confirmed Attack Rate and Qualifying Attack Rate vs Qualifying Attack Rate	FAS
14.2.1.11	KM Plot of Time to First Attack after Last Dose	FAS
14.2.1.12	KM Plot of Time to First Attack after First Dose	FAS
14.2.1.13	KM Plot of Time to Treatment	FAS
14.2.1.XX	Correlation Plots of AE-QoL, DASS and Confirmed Attack endpoints (will plot the domains with significant correlation at P<0.10)	FAS
Pharmacokinetic Analysis		
14.2.2.1	Mean Plasma BCX7353 Concentration-time plot –linear Scale	PK
14.2.2.2	Mean Plasma BCX7353 Concentration-time plot – semi-logarithmic scale	PK
14.2.2.3	Median Plasma BCX7353 Concentration-time plot –linear Scale	PK
14.2.2.4	Median Plasma BCX7353 Concentration-time plot – semi-logarithmic scale	PK
14.2.2.5	Individual Plasma BCX7353 Concentration-time plot –linear Scale	PK
14.2.2.6	Individual Plasma BCX7353 Concentration-time plot - semi-logarithmic scale	PK
14.2.2.7	Mean Trough Plasma BCX7353 Concentration-time plot –linear Scale	PK
14.2.2.8	Median Trough Plasma BCX7353 Concentration-time plot –linear Scale	PK
14.2.2.8	Individual Trough Plasma BCX7353 Concentration-time plot (line plot)	PK

Figures	Title	Population
Pharmacodynamic Analyses		
14.2.3.1	Plot of Mean Ex-vivo Kallikrein Inhibition - Time Profile by Treatment	PD
14.2.3.2	Plot of Individual Ex-vivo Kallikrein Inhibition - Time Profile by Treatment	PD
14.2.3.3	Plot of Least Squares Mean of Treatment Differences from Placebo in Ex-vivo Kallikrein Inhibition	PD
Pharmacokinetic/Pharmacodynamic Analyses (PK-PD include subjects with measurements for both PK-PD)		
14.2.4.1	Plot of Plasma Kallikrein Inhibition and Plasma BCX7353 Concentration	KKI PD
14.2.4.2	Exposure-response Analysis of Ex-vivo Kallikrein Inhibition	KKI PD
14.2.4.3	Plot of Plasma Kallikrein Inhibition by Attack Free Status	KKI PD
